In an earlier published retrospective review of 63 liver transplant recipients involving 73 OLT procedures, the use of Thymoglobulin® compared with a group not using Thymoglobulin® as part of induction therapy was evaluated.⁵⁰ Standard triple therapy included cyclosporine, azathioprine and prednisone. The data analyzed included patient survival, graft survival, rejection episodes, time to first rejection episode, hematological parameters, and infectious complications. Fifty-seven OLT procedures were induced with Thymoglobulin® plus triple therapy and 16 received triple therapy alone. All retransplants were performed under Thymoglobulin® induction. Three to 6 vials (25 mg/vial) of Thymoglobulin® were administered via IV infusion each day. Dose adjustments were based on WBC and platelet counts. Doses were held when platelets were below $30,000 \times 10^6/\text{mL}$, and/or WBC count was below $2500 \times 10^3/\text{mL}$. Fever (61%), thrombocytopenia, anemia, and leucopenia were the most common AEs reported with Thymoglobulin® induction therapy. These AEs were managed by dose reduction or drug administration on alternate days. Infectious complications were similar in both groups. Rejection episodes occurred less frequently in the Thymoglobulin® group (n = 33, 58%) when compared with the triple therapy control group

(n = 12, 75%). Rejection in the Thymoglobulin® group occurred later after transplantation, at a median of 51 days, compared to 11.5 days in the control group (p <0.05). Occurrence of rejection while patients were on Thymoglobulin® was low, (7%), compared with the control group, (50%). However, patient and allograft survival at one year was slightly lower in the Thymoglobulin® group, (84% and 68%, respectively), compared with the control group, (94% and 81%, respectively). Although, in general, patients who ultimately received Thymoglobulin® were more ill prior to transplant, based on their need for ventilator support (21% vs. 0%), ICU status (37% vs. 12%), and renal dysfunction (11.8% vs. 8.1%), prior to transplantation. This retrospective study demonstrated that Thymoglobulin® as part of induction therapy resulted in a lower incidence of graft rejection during the first 30 days post-transplant and a longer graft survival time before first rejection. In addition, Thymoglobulin® allowed for the delay of initiation of cyclosporine therapy for up to 3 weeks post-transplant, without an increase in infectious complications.

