- Biopsy-proven acute allograft rejection rates at 6 Months and 12 Months post-transplant.
- AKI (Stage 3 rates) at 3 Months post-transplant
- Renal function measured by eGFR at 12 Months post-transplant
- Microbiologically-proven systemic infection rates at 6 Months and 12 Months post-transplant
- Hepatitis C viral loads (in HCV positive recipients) at 12 Months post-transplant
- Incidence of biopsy proven recurrence of HCV infection at 12 Months post-transplant
- Incidence of AEs and SAEs at 12 months post-transplant

For each efficacy event, simple event rate estimates (proportion of events) at 12 months will be obtained, and event rates between the two treatment groups will be compared using Z-statistic based, two-sided, 95% confidence interval for RC – RE, where RC and RE are the event rates for the Early CNI treated Control Group and the Late CNI Initiated/Thymoglobulin® Study Group, respectively. In addition, for the composite efficacy endpoint and its components, individually, Kaplan-Meier survival methods will be used to estimate probabilities of efficacy events by visit. Greenwood’s formula will be used to estimate standard errors and to derive the two-sided, 95% confidence interval of RC – RE, by visit window. HCV replication in HCV positive patients will be compared with summary statistics.

Due to the short duration of study involvement, we expect very few patients to be lost to follow-up, or to withdraw consent. Therefore, for the composite efficacy endpoint, patients who are discontinued from the study for these two reasons, (prior to the incidence of death, graft loss, or biopsy-proven acute cellular rejection), will not be considered as efficacy failures. If there are an adequate number of subjects from each clinical center, a formal test of center by treatment interaction effect will be made.

Adverse Events (AEs) / Infections:

Generally, infections are analyzed together with Adverse Event data. **In addition, infections will be analyzed separately. Infections will be documented on both, the Infection CRF and the AE CRF.** The data collected on both CRFs will be coded with the MedDRA dictionary which gives preferred term and body system information.

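### A Kaplan-Meier curve for rejection alone, with no competing-event rule, would by default censor death and re-transplantation and modestly overstate the probability of rejection

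*Combined protocol and SAP*

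**What the plan says.** All references are to the combined protocol and SAP. The analysis text is in Study Endpoints / Efficacy and Safety, section C (Additional Efficacy and Safety Variables for Evaluation).

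- Crude analysis: "For each efficacy event, simple event rate estimates (proportion of events) at 12 months will be obtained", with a Z-based 95% interval for RC – RE (Early CNI control minus Thymoglobulin).
- Time-to-event analysis, added to the crude one: "for the composite efficacy endpoint and its components, individually, Kaplan-Meier survival methods will be used to estimate probabilities of efficacy events by visit". Greenwood's formula supplies the standard errors and is used "to derive the two-sided, 95% confidence interval of RC – RE, by visit window".
- Components: the composite is not formally defined here. The next paragraph, on patients lost to follow-up or withdrawing consent, refers to discontinuation "prior to the incidence of death, graft loss, or biopsy-proven acute cellular rejection". These are the only components named. The renal composite under Overall Study Design is a different endpoint.
- Rejection variables: ACR at 30 days is a secondary endpoint, and section C lists "Biopsy-proven acute allograft rejection rates at 6 Months and 12 Months post-transplant".
- Graft loss (Efficacy and Safety Assessments, section C) means re-transplantation or death.
- Follow-up: the section on Study Drug Discontinuation lists graft loss and death among the reasons a patient leaves the study early.
- Missing data: the section on Missing Values/Censoring/Discontinuations covers LOCF at Day 30 and missing baseline creatinine. It gives no rule for death or re-transplantation in a rejection curve. No competing-risk method appears anywhere in the document.

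**The concern.** Kaplan-Meier treats a censored patient as someone who could still have the event. That is reasonable for a patient who moves away. It is wrong for one who has died, or whose graft has been replaced, without rejecting. Such a patient cannot go on to reject that graft, yet Kaplan-Meier spreads the patient's weight over those who remain and may reject later. One minus Kaplan-Meier then estimates rejection in a hypothetical population with no deaths or re-transplants, and this exceeds the proportion of transplanted patients who actually reject.

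Rejection is the only named component with this problem. Death is itself an event in the death curve, in graft loss (by definition) and in the composite.

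Graft rejection is the first secondary objective, because it is the obvious risk of withholding the CNI for 10 days. The Kaplan-Meier difference is to be reported at every visit window, while section C gives crude proportions only at 12 months. At 12 months the plan would produce two estimates of the same rejection difference that can disagree even with complete follow-up, and it does not say which governs.

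**Working it through.** The plan gives no figure for the rejection curve, so there is none to reproduce. The check compares the two estimators.

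**1. Illustration with complete follow-up (invented counts).** Of 55 patients, 8 die by Day 30 without rejecting, and 14 of the other 47 reject later.

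- Proportion who reject: 14/55 = 25.5%.
- Kaplan-Meier with deaths censored: 47 remain at risk, so 1 – 33/47 = 14/47 = 29.8%.
- Excess: 4.3 points.

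This shows the mechanism. It is not a forecast, since 8/55 = 14.5% dying by Day 30 with every rejection after that is deliberately heavy.

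**2. Size under plausible inputs.** Let F(t) be the rejection distribution if nobody died or was re-transplanted, and G(t) the probability of being free of death and re-transplantation at t, with the two independent.

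- One minus Kaplan-Meier estimates F(t).
- Cumulative incidence: CIF(t) = ∫₀ᵗ G(u) dF(u).
- Excess: F(t) – CIF(t) = ∫₀ᵗ [1 – G(u)] dF(u). It is never negative, and is positive as soon as any loss precedes a possible rejection.

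Inputs:

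- Timing: the retrospective series of 73 procedures under Efficacy of Thymoglobulin in Liver Transplantation. "Rejection in the Thymoglobulin® group occurred later after transplantation, at a median of 51 days, compared to 11.5 days" in controls. I take F(t) = q(1 – e^(–λt))/(1 – e^(–365λ)), with λ set so that half of F(365) falls by 51 days (λ = 0.0134) or by 11.5 days (λ = 0.0603).
- Rejection: 28–30% at 12 months in both arms (assumed; the 298-patient series in the Introduction had 72% freedom from rejection with Thymoglobulin, i.e. 28%). q is solved so that CIF(365) equals this.
- Losses: 11–16% by 12 months, equal in the arms (assumed; 89% graft survival in the steroid-free randomized study and 84% one-year patient survival in the 73-procedure series are cited).
- Loss timing: half by Day 60, constant hazard before and after (assumed).

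Excess of one minus Kaplan-Meier over cumulative incidence, in percentage points:

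| 12-month rejection | Loss | Late arm, 12 mo | Early arm, 12 mo | Late arm, Day 30 | Early arm, Day 30 |
|---|---|---|---|---|---|
| 28% | 11% | 1.27 | 0.43 | 0.13 | 0.24 |
| 28% | 16% | 1.89 | 0.63 | 0.19 | 0.35 |
| 30% | 11% | 1.36 | 0.46 | 0.14 | 0.26 |
| 30% | 16% | 2.03 | 0.68 | 0.21 | 0.38 |

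At 12 months the spurious contribution to RC – RE is 0.8 to 1.4 points (for example 1.27 – 0.43 = 0.84; 2.03 – 0.68 = 1.35). At Day 30 the larger excess is in the early-rejection arm.

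**3. Sensitivity of the ordering.** Here loss follows a Weibull distribution, rejection figures are treated as F(365), and timing is as above.

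- Rejection of 58% vs 75% (the 73-procedure series), equal loss of 10–15%, constant to moderately front-loaded (shape 1 to 0.5): excess 1.2–3.6 (Thymoglobulin) vs 0.4–2.3 (control). RC – RE is 17.0 points by Kaplan-Meier and 17.8–18.3 by cumulative incidence.
- Rejection of 28% vs 50% (the 298-patient series), 10% loss strongly front-loaded (shape 0.3): 1.58 vs 1.83, order reversed.
- Same rates, constant hazard, loss of 5% with Thymoglobulin and 15% in control: 0.28 vs 0.37, order reversed.

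**4. Against sampling error.** SE(RC – RE) = √[p₁(1 – p₁)/55 + p₂(1 – p₂)/55].

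- 28% in both arms: √(2 × 0.2016/55) = 8.6 points.
- 28% vs 50%: √(0.2016/55 + 0.25/55) = 9.1 points.

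**The case against.** The case for leaving the text alone has real substance.

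- **An unaffected estimate is already planned.** The crude 12-month proportion does not depend on how deaths are censored and, with complete follow-up, equals the cumulative incidence. Kaplan-Meier is an addition to it. This stands, and it means a Kaplan-Meier artefact could not create a 12-month difference unnoticed. It does not cover the other visit windows, for which section C names no crude comparison.
- **Censoring is inferred.** No sentence says deaths are censored in the rejection curve, and the components come from a parenthesis. This also stands, so the point is put as the default reading. With Kaplan-Meier prescribed per component and no competing-event rule, censoring is what an analyst would ordinarily do.
- **The effect is small.** It is about 1 point in RC – RE against a standard error of about 9, in a Phase 2 trial sized on creatinine. That stands as well. It limits the importance of the point but does not make the estimator right.

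A reader might infer something stronger: that the overstatement is generally larger in the Thymoglobulin arm, because its rejections come later. The documents do not support that. The ordering depends on the horizon, the rejection rates and the size and timing of losses, and it reverses at Day 30, the time of the secondary rejection endpoint. The late-timing premise rests on one retrospective, cyclosporine-based series of 57 vs 16 procedures.

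Nor should that series' one-year graft survival (68% vs 81%) be used to claim a spurious gap of about 3.5 points. Its Thymoglobulin patients were sicker beforehand (ventilator support 21% vs 0%), and every re-transplant was done under Thymoglobulin. The randomized pilot of this regimen found no difference in one-year patient and graft survival, and the steroid-free randomized study had 89% graft survival in both groups.

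**Conclusion.** The point holds as a modest but definite defect in one planned curve. If death and re-transplantation are censored, as the text implies by default, the rejection-only Kaplan-Meier estimate is too high whenever losses precede later rejections, and the Greenwood interval for RC – RE is built on that estimate.

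Under equal 12-month losses of 11–16%, 28–30% rejection, the cited rejection timing, half of losses by Day 60 and independence of loss and rejection, the 12-month excess is about 1–2 points with late rejection and 0.4–0.7 with early rejection. At Day 30 it is 0.1–0.2 and 0.2–0.4 respectively. It can therefore differ between arms, in a direction that cannot be fixed in advance. It is small beside a standard error of about 9 points.

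The crude 12-month proportions and the composite, death and graft-loss curves are not affected. The change is worth making because the error is systematic, concerns the outcome of the first secondary objective, and is easily removed.

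**What to change.** In Additional Efficacy and Safety Variables for Evaluation:

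1. Keep Kaplan-Meier with Greenwood intervals for the composite, patient survival and graft survival.
2. For biopsy-proven rejection, use the cumulative incidence function (Aalen-Johansen), with death and re-transplantation before rejection as competing events. Form RC – RE and its 95% interval at each visit window from that estimator's variance.
3. State that only loss to follow-up, withdrawal of consent and end of follow-up are censored in the rejection analysis, and list the composite's components explicitly.

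The cost is a few sentences and a standard procedure. No new data are needed, because rejection, graft loss and death are already recorded on the case report forms. The sample size is unaffected.

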C. Number of Patients: One hundred and ten (110) liver transplant recipients will be enrolled in this study, **approximately** 40-50 patients at Cleveland Clinic, (the lead center), and 15-25 patients at each of the three additional participating centers (number of enrollment may vary at different centers).

Sample size estimates for study of liver dysfunction

Sample sizes were computed on the bases of using Welch’s two-sample t-tests to compare changes in creatinine between the control and the thymo 4.5 groups. Assumptions regarding differences in means and standard deviations for each group were based on the results of preliminary data and are given in Table 3. The smaller of the two standard deviations was varied along a range from that observed in the preliminary data to being equal to the larger standard deviation. The former would tend to yield smaller sample sizes, while the latter larger. Assuming that 10% of the patients that are initially enrolled will drop-out before 12 months values are measured, the sample sizes indicated should be increased by 10% to account for this drop-out.

These calculations were done using SAS software (version 9.3, Cary, NC). A significance level of 5% and two-tailed tests were assumed for all testing.

For delta creatinine, we are assuming a difference in means between groups of 0.32. In the pilot data delta creatinine in the control group had a standard deviation of 0.51, while the thymo 4.5 group a standard deviation of 0.12. Therefore, three levels of standard deviation—0.12, 0.32, and 0.51. Based on these calculations, enrolling enough patients to meet the sample size requirements for detecting differences in delta creatinine (within 2 SD, 0.32) will mean having ample sample size for detecting differences in month 12 GFR. Accordingly, we noticed that a sample size of 110 (55 in each group) would give us 90% power with the safest margin for 10% dropouts throughout the study.

Table 3. Minimum sample sizes need to achieve desired levels of power

Comparison	Difference	SD1	SD2	Power	
				80%	90%
Delta Creatinine	0.32	0.51	0.12	46	60
			0.32	58	78
			0.51	82	110
Month 12 GFR	36.8	26.6	20.5	16	20
			23	18	22
			26.6	20	26

D. Selection of Study Population:

INCLUSION CRITERIA

- Patients undergoing deceased donor solitary liver transplantation.
- Age 18 – 75 years at the time of transplantation.
- Willingness and ability to comply with the study procedures.
- Signed Informed Consent Form.

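### The 12-month composite comparison counts lost and withdrawn patients as non-failures in a simple proportion with no stated denominator, so it is biased by dropout, modestly and in a direction the plan leaves open

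*Combined protocol and SAP*

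**What the plan says.** Under Study Endpoints, part C (Additional Efficacy and Safety Variables for Evaluation), for each efficacy event "simple event rate estimates (proportion of events) at 12 months will be obtained". The arms are compared through a "Z-statistic based, two-sided, 95% confidence interval" for the control rate minus the Thymoglobulin rate. For the composite and each of its components, "Kaplan-Meier survival methods will be used to estimate probabilities of efficacy events by visit", with Greenwood standard errors and a second interval for the same contrast. This is described as additional. No censoring rule is given, and nothing says which interval leads.

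The next paragraph adds that "for the composite efficacy endpoint, patients who are discontinued from the study for these two reasons" before death, graft loss or biopsy-proven rejection "will not be considered as efficacy failures". The two reasons are loss to follow-up and withdrawal of consent. The rationale is that involvement is short and "we expect very few patients to be lost to follow-up, or to withdraw consent".

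The sample size text (Investigational Plan, part C, Number of Patients) plans differently: "Assuming that 10% of the patients that are initially enrolled will drop-out before 12 months values are measured". Withdrawn patients are not replaced (Early Patient Withdrawal), and the study is open-label (Treatment Blinding). The section on missing values covers day-30 measurements and baseline creatinine, not 12-month events.

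**The concern.** A simple proportion has no place for an unknown outcome. A patient who leaves at month 3 without an event either stays in the denominator as a success or is removed, and each choice biases the 12-month risk. The plan's wording points to the first choice, so unknown outcomes would be scored as favourable. In an open-label trial the reasons for leaving may differ by arm, and the arm that loses more patients would then look better.

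The stated rationale does not settle the matter. Follow-up for these events is 12 months, not 30 days, and the plan itself allows for 10% dropout by then. With two planned intervals for the same contrast and no order between them, the choice could also be made after the results are seen.

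**Working it through.** **Inputs from the documents.** 55 patients per arm; 10% dropout before 12 months, which is 0.10 × 55 = 5.5 patients per arm; the simple proportion and the Kaplan-Meier estimate, both at 12 months.

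**Assumptions.** The documents give no composite event rate, so true 12-month risks of 10% to 40% are assumed. They give no dropout by arm, so 5% versus 15% is illustrative. Dropout is taken as independent of outcome.

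**The plan's own figure.** None exists for the event proportions. The sample size of 110 (difference 0.32, both SDs 0.51, two-sided 5%) reproduces under Welch's test with 90.3% power. This point does not affect it.

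**Step 1: lost patients kept as event-free.** Let p be the true risk and d the dropout risk, with λ = −ln(1−p) and μ = −ln(1−d). Under constant hazards:

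expected proportion = λ/(λ+μ) × [1 − (1−p)(1−d)]

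For p = 0.30 and d = 0.10: λ = 0.3567, μ = 0.1054, giving 0.772 × (1 − 0.63) = 0.286. If all dropout precedes any event, the expectation is p(1−d).

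| True risk | Reported, constant hazards | Bias (points) | Reported, all dropout early | Bias (points) |
|---|---|---|---|---|
| 10% | 9.5% | −0.5 | 9.0% | −1.0 |
| 20% | 19.0% | −1.0 | 18.0% | −2.0 |
| 30% | 28.6% | −1.4 | 27.0% | −3.0 |
| 40% | 38.1% | −1.9 | 36.0% | −4.0 |

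If events are front-loaded (Weibull shape 0.5), the bias shrinks to −0.3 to −1.2 points.

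**Step 2: effect on the comparison.**
- Equal 10% dropout, true 30% versus 15%: the 15.0-point difference becomes 14.3 (13.5 if all dropout is early).
- No true difference at 30%, dropout 5% control versus 15% Thymoglobulin: 29.3% versus 27.8%, a false 1.5 points. With front-loaded events it is 29.54 − 28.59 = 0.95. With all dropout early it is 28.5 − 25.5 = 3.0.

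**Step 3: lost patients excluded.** At p = 0.30 and d = 0.10, the share lost before an event is μ/(λ+μ) × 0.37 = 0.084. The proportion becomes 0.2856/(1 − 0.0844) = 31.2%, an upward bias of 1.2 points. With 5% versus 15% dropout it gives 30.6% versus 31.9%, so the arm that loses more now looks worse by 1.3 points. The direction depends on the denominator.

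**Step 4: Kaplan-Meier.** In 20,000 simulated arms of 55 with lost patients censored and 10% dropout, the mean estimate was 20.0% for a true 20% and 29.9% for a true 30%.

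**Step 5: scale.** The standard error of the difference at 30% is √(2 × 0.3 × 0.7/55) = 8.7 points, with a 95% half-width of about 17. A 1.5-point shift is about 0.17 standard errors, or 0.015 × 55 = 0.8 of a patient. It moves two-sided type I error from 5% to about Φ(−1.79) + Φ(−2.13) = 5.3%. By contrast, counting 5.5 lost patients as failures would raise an arm's rate by up to 5.5/55 = 10 points, and no planned analysis would show that.

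**The case against.** The strongest reply is that the plan already contains the remedy. Kaplan-Meier with Greenwood intervals is specified for the composite and its components. The disputed sentence follows that text, and not treating a patient as a failure is compatible with censoring. This stands in part: event-free counting is the natural reading in a simple proportion, but not the only one. It does not supply a censoring rule or say which interval leads.

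Other limits also stand:
- A reader might infer that every 12-month event rate is biased downward. The rule is written for the composite only and for two reasons only. No rule is stated for single components or for other withdrawals, and the denominator is not given.
- A reader might infer that the trial's main result, or 6-month survival, is compromised. The primary endpoints are at 30 days with their own missing-data rule, and the simple proportion is specified at 12 months.
- A reader might take the 10% as a flat contradiction of the low-loss rationale. It belongs to a creatinine and GFR calculation and is not broken down by reason. It may include deaths, graft losses or investigator withdrawals, so it is an upper planning figure for loss and withdrawal.
- Stopping treatment is not leaving the study, and one-year status is requested for each randomized patient (Study Completion and Post-Study Treatment). This limits unknown outcomes without removing them.
- Kaplan-Meier is itself biased if leaving is related to outcome, so it needs a sensitivity analysis beside it.

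**Conclusion.** The point holds as a defect in the 12-month composite analysis: a rule that scores unknown outcomes as non-failures, an unstated denominator, no censoring rule, no order between two intervals, and a rationale that fits poorly with 12-month follow-up and the sample size assumption. With lost patients kept in the denominator, the downward bias at 10% dropout is about 0.5 to 1.9 points under constant hazards and at most 4 points in the early-dropout case. Unequal dropout of 15% versus 5% at a 30% rate favours the arm with more loss by about 1 to 3 points. These sizes rest on assumed event rates, an assumed imbalance and non-informative dropout.

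The documents do not support a claim that dropout will differ by arm, or that this bias alone would change a conclusion, since the sampling error is several times larger. The change is worth making because the better estimate is already planned and the present wording leaves even the direction of bias open.

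**What to change.** Amend part C of the Study Endpoints section to:

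1. Define the composite (death, graft loss or biopsy-proven rejection). It is only implied there and is not in the endpoint lists. The one composite named elsewhere, under Overall Study Design, is renal.
2. Make the 12-month Kaplan-Meier risk difference with its Greenwood 95% interval the main comparison for the composite, death and graft loss. Censor lost or withdrawn patients at last contact, and say how other withdrawals are handled. Death already counts as graft loss in the protocol's definition, so it is not a competing event for these outcomes.
3. For rejection alone, use cumulative incidence with death as a competing event.
4. Keep the simple proportion as a sensitivity analysis with a stated denominator and best-case and worst-case counts for those lost, because censoring may be informative in an open-label trial.
5. Replace the rationale about short involvement and few losses with one consistent with the dropout assumed for sample size.

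The cost is a slightly wider interval and a little more analysis work. No extra patients or visits are needed.
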